5.6.2 Overview of Anthropometric and Clinical Procedures

Collection of medical, concomitant medications, anthropometric assessments (weight, height, BMI) and clinical assessment for physical signs of malnutrition will be performed per the SOEs. The questionnaires will be brief enough not to add undue respondent burden.

5.6.3 Overview of Planned Neurodevelopment assessments .

The KABC-II (comprehensive cognitive testing), TOVA (attention, impulsivity), CogState (working memory and learning cognitive screening) have all been validated in the Ugandan context ¹¹ and as such they are all represent "gold standard" assessments for Uganda in their respective neurocognitive domains; particularly in the absence of any normative data for any such tests for Uganda.

In fact, in the context of pediatric HIV in Africa, the KABC is the best validated comprehensive cognitive performance task available.

These tests (KABC-II, TOVA, CogState, and CBCL) are described in detail below. We used these tests previously to evaluate the neuropsychological gains from CCRT training in Ugandan children with HIV,^{1,5,6} the effects of HIV Clade I subtype on neuropsychological outcomes³⁸, and neuropsychological effects of HIV on treatment-naïve Ugandan children with high CD4 counts.³⁹ These tests have also been used to evaluate cognitive gains from CCRT intervention for Ugandan children surviving cerebral malaria.^{21,25,26} and they have been validated in the P1104s study.²⁴

Kaufman Assessment Battery for Children (second edition). Used in both the PROMISE NeuroDev study with the HEU and HUU cohorts, and in P1104s with HIV+ children, the KABC-II will be the principal test for cognitive ability.⁴⁰ It is validated in sub-Saharan Africa⁴¹⁻⁴⁴ and has been adapted for pediatric HIV research.^{1,6,39,45-48} Using the Luria model for neuropsychological assessment within KABC-II, the primary outcome variables are the global scores of Sequential Processing (memory), Simultaneous Processing (visual-spatial processing and problem solving), Learning (immediate and delayed memory), Planning (executive reasoning), Delayed Recall, Nonverbal Index (NVI) subtests not dependent on understanding instructions in English, and Mental Processing Index (MPI), a composite of all the cognitive performance areas.

Test of Variables of Attention (TOVA). TOVA is a computerized visual continuous performance test used in to screen, diagnose and monitor children and adults at risk for ADHD.⁴⁹ TOVA consists of the rapid (tachistoscopic) presentation of a large geometric square on the computer screen with a smaller dark box either in the upper position (signal) or lower position (non-signal). The child is asked to press a switch held in the preferred hand as fast as possible in response to the signal (measuring vigilance attention), but to withhold responding to the non-signal (measuring impulsivity). Following spoken instructions in the local language and practice trials, TOVA takes ~11 minutes for children 5 to 5.5 years old, and 22 minutes to administer for children 5.5 years and older. TOVA had been adapted for pediatric HIV research in Uganda.^{1,5,6,38,39} TOVA's primary outcome variables are response time variability (a sensitive indication of inattention), response time, percent commission errors (impulsivity), percent omission errors (inattention), an attention deficit hyperactivity disorder (ADHD) index score (missed signals in proportion to incorrect responses to non-signal), and a D prime signal detection measure of overall test performance (correct signal "hits" in proportion to correct non-responses to non-signal).

CogState.^{50,51} We used this computerized neurocognitive assessment in our prior CCRT studies.^{26,52} CogState presents a 30-min session that includes playing cards in a game-like manner to assess memory, attention, discrimination learning, and executive function that is non-language dependent. CogState tests include Card Detection (simple reaction time), Identification (choice reaction time), One-Back Working Memory, and One-Card Learning. CogState also includes the Groton Maze Task, which can measure visual-motor tracking (Maze Chase) and executive functioning/planning (Maze Learning). CogState is available on tablets, but its assessment data must be uploaded via the internet, and assessment results downloaded from CogState's central server. CogState has strong correspondence validity with KABC-II and TOVA. These three are the trilogy of our gold standard.²⁸

Achenbach Child Behavior Checklist (CBCL). This is NOT part of the neuropsychological gold standard, but is an important parent-based screening tool for emotional and behavioral problems observed in the child. The CBCL is important to assess when a child's social environment is enriched by adult oversight in game assessment and training, reflecting a collateral training benefit.²¹ the CBCL has been translated and adapted in our severe malaria research in Kampala⁵³ and Blantyre^{54,55} and structure validated for use with HIV-affected children³⁵ for the PROMISE ND study and pediatric HIV research in Uganda,^{56,57} and in CCRT intervention studies in Uganda.^{5,6,26} Our principal outcomes are Internalizing, Externalizing, and Total symptoms.

Quality of Home Environment and Caregiving. We will use the middle childhood version of the Caldwell Home Observation for the Measurement of the Environment (HOME) validated for use as an important distal measure predictive of our gold standard assessments.^{58,59} The HOME assesses the stimulation and learning opportunities offered by the child's home environment. Along with HOME, we will also use a socioeconomic evaluation scale of physical quality of the home environment (SES score) also used with Ugandan children and sensitive to long-

term (distal) neurocognitive outcomes such as the KABC-II.⁶⁰

Hopkins Symptom Checklist -25 items. The HSCL is a 25-item self-response questionnaire that will be used to evaluate depression and anxiety symptoms in caregivers .This questionnaire has shown adequate performance in Ugandan populations ^{34, 36}. Questions are scored in a severity scale from 1 to 4, with higher scores indicating more symptoms of distress.

5.6.4 Overview of CD4+ T-cell counts, immune activation, and viral load assessments (HIV cohort only)

[figure not shown]
As part of their standard of care (HIV cohort only), CD4, CD8, viral load and other immunology measures will be available from a blood draw taken within a week from the time of neuropsychological assessment as a more proximal predictor of disease effects on assessment performance. CD4 and CD8 T-cell activation level testing will be performed on EDTA anti-coagulated whole blood using a fresh-lyse/no-wash flow cytometry procedure. Blood will be incubated with monoclonal antibodies including CD3, CD8, CD4, CD38, and HLA DR, then processed and acquired on a multi-laser bench top flow cytometer. For each run of patient samples, a separate sample of stabilized blood product (CD-Chex, Streck Labs) is processed. CD4 T cell and CD8 T cell activation levels will be defined as % CD38 and HLA-DR co-expression.⁶¹

5.6.5 Overview of Brain Powered Games

The BPG subtests were designed/selected based on what has been validated from the attention/working memory/visual-spatial categorization and analysis subtests validated in previous CCRT clinical trials work from BrainTrain Captain's Log ¹. However, Captain's Log was proprietary and not available for transition to scale for LMICs in Africa. Furthermore, it is no longer available or supported, and its successor has not been tested in Uganda. BPG is designed to address the very same cognitive skills as Captain's Log Uganda was, but is scalable, accessible and affordable for the African context. Additionally, BPG has been previously proven to improve neurocognition among Ugandan children with HIV¹⁸.

Each BPG game includes a visual tutorial, several adjustable settings on the administrative side (Admin), and records game play data for research purposes. As part of a current preliminary study using BPG with aging Ugandan adults with HIV, we have now adapted BPG as a mobile app for the touch screens of tablets and smart phones, as part of a preliminary study of BPG dynamic assessment in aging adult HIV patients in Uganda. Our preliminary findings thus far have documented that the neuropsychological gain scores from pre- to post-training with BPG are sensitive to the clinical and health parameters of our patients at enrollment, including ARV adherence, viral load, adverse health events, and CD4 nadir. We will also use gain scores pre- to post-training for our gold standard of neuropsychological tests as our principal performance outcomes in the present study, as noted in Table 3 (far right column) for each of the BPG training games below.

Butterfly. Here a butterfly flies across the screen and the child touches it when the butterfly stops moving. When the child touches the butterfly, the child earns 10 points, the butterfly moves somewhere else on the screen, and the process is repeated. The game continues until the child scores a set number of points. Butterfly serves as a training exercise, letting a child become familiar with the game interface on the tablet.

iSpy. This is a memory game. iSpy shows the child a scene with several objects. After a few seconds in which the child is supposed to memorize the objects, iSpy removes the scene. A few seconds later the scene reappears — but now with a new object. The child must recall which objects were in the previous scene

and touch the new one before iSpy again takes the scene away. The game progresses with one more object every time the scene reappears, and the child is challenged to recall which objects have been seen before. iSpy has another mode in which objects are removed from the scene and the child has to remember where the missing object used to be.

Stampede. Another memory game, Stampede shows the child an animal to remember. A group of animals, including the one the child has been shown, runs across the screen. The child must touch the featured animal before it moves all the way across the screen. The number of animals that appear is based on the current round and the admin settings. As the game progresses, the child is given an increasing number of animals to remember and touch before they run across the screen.

Figure 5. The BPG Spatial Navigation Learning game was just added to the package and field tested with HIV patients at the MUJHU Kampala study site in July/August 2016. In this game the child "moves" about in a virtual maze with pictures of common African animals at intersections. Performance gains (correct turns, time to complete maze to obtain prizes) are

Whacky Animal. Whacky Animal is a memory game inspired by whack-a-mole. Similar to Stampede, the child is shown an animal to remember at the beginning of the round. A random animal then pops up from the sides of the screen and the click must touch the animal before it ducks behind the edge.

Spatial Navigation Training (SNT; Figure 5). This is BPG's newest game, piloted in Uganda for the first time in June, 2016 with adults and also with children with HIV. SNT involves a relatively new approach to cognitive training that uses a procedure (spatial navigation) that is localized to the hippocampus, the area most involved with visual-spatial memory and learning.⁶² Spatial navigation is getting increased emphasis in computer gaming because spatial navigation training generalizes to other aspects of verbal and visual learning and memory performance. In this game the child "moves" about in a virtual maze with pictures of common African animals at intersections (Figure 5). SNT stimulates not only the hippocampus, but also other mobility-related brain areas (similar to what happens in imaging studies when a person is asked to imagine walking).¹⁴ In two recent publications, Co-I [name] and colleagues showed that after 12 sessions of SNT, older adults demonstrated improvements in both executive functioning and more complex aspects of mobility.^{15,16} SPN is presently being used by [name] and [name] in a pilot study with aging HIV adult patients in Uganda.

Village Builder (VB). [name] and his MSU-GEL team will develop a game emphasizing social cooperation (prosocial) and emphasizing reasoning and planning skills. This executive function game will use the same African village motif and animals in the existing BPG package. However, it will differ in that children will use their avatars in a cooperative manner to add dwellings to the village and domesticated animals (livestock such as goats, cattle, pigs, chickens) to the surrounding village compounds so as to increase the available resources in a positive manner.

Unlike the existing games in Africa BPG that emphasize vigilance attention, monitoring and working memory, and visual spatial learning and navigation (mazes task), this new Village Builder game will emphasize executive function and reasoning in children. It will be intuitive, culture-fair, non-violent, and designed to be engaging for the computer novice and casual gamer. [name] has served as a consultant on NIH application to develop a touch screen Android Tablet assessment game package for assessment of executive functioning in preschool-age children, called "EF Touch". This app has undergone pilot testing with Kenyan children 4 to 6 years of age.⁶³ Using a model of EF development based on self-control interventions, pro-social values, and validated in early and middle childhood in terms of social and academic outcomes,⁶⁴ [name], [name], and [name] will work together to incorporate the best validated response features of EF Touch (Animal Go/No-Go, Silly Sounds Stroop, Pick the Picture)⁶³ into the new Village Builder EF game. The eventual goal is to compare the dynamic versus static BPG cognitive assessment features when they emphasize attention, memory, and learning tasks and when they emphasize planning and reasoning tasks in school-age children. Both types of BPG games (attention/memory/learning versus planning/reasoning) will also be compared to the gold standard of tests presently validated for the study sites (KABC/TOVA/CogState) in terms of their comparative sensitive to more proximal (HIV exposure and treatment) and distal (nutrition and quality of caregiving and home environment)

risk factors.

By comparing Village Builder executive function (EF) game to the existing Africa BPG package, we can better understand what value it adds in terms of a static and dynamic assessment of brain/behavior function in younger school-age African children. At present, no such CCRT intervention or assessment program exists that has been validated for African children, despite the great importance of EF in frontal lobe brain development at this stage of middle childhood. EF and frontal lobe development are vitally important precursors for future neurocognitive adaptation and function in children affected by HIV (e.g., self-management, impulsivity, planning, treatment adherence, psychosocial adjustment and prosocial behavior) as they age into adolescence and eventually into early adulthood.

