Primary Outcome: To establish the validity of BPG as a measure of neurodevelopment in at-risk children. (e.g. HIV affected) To establish BPG as a neurocognitive “stress test” or medical “challenge” test, in order to evaluate brain/behavior functional integrity in HIV-affected children.

Exposure Variables of Interest:

- HIV status (HEU, HIV+, HUU)
- Other clinical risk factors for poor neurodevelopment (child’s weight, height, HIV disease and immunological factors)

CULTURE SPECIFIC NEURODEVELOPMENT ASSESSMENT OF HIV-AFFECTED CHILDREN STUDY

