5.0 NEURODEVELOPMENTAL ASSESSMENT PROTOCOL DESIGN

5.1 Overview of Study Design:

[figure not shown]
Static and Dynamic Assessment Process for Each Study Child. Figure 6 provides an overview of study visits and assessments. Following enrollment and physical and medical exams, each child will return to the clinic with their principal caregiver for a half-day of gold standard neuropsychological assessments (KABC-II, TOVA, CogState). At this time the caregiver will complete the Achenbach CBCL questionnaire for school-age children, the Caldwell HOME scale, the SES material possessions evaluation, and the Hopkins Symptom Checklist-25 (caregiver psychological well-being). We will explain assessments and provide instructions in the local language. Study assessments will proceed in two phases. In Phase I, children will be randomized to start BPG trainings (50% of sample) or to a wait-list condition. Within a week after baseline assessment, the full sample of children will be contacted by a field research assistant and facilitate a first BPG session. This first session will be completed by the full sample because it will be considered as an internal performance evaluation session with BPG and will be completed on a tablet, supervised by the field research assistant. This will be done as part of the 50-60 minutes training session on the 5 BPG games (about 10 minutes per game), and will constitute the BPG static assessment. Thereafter, the field research assistant will return with children allocated to the BPG trainings (50% of sample) at a convenient time and supervise BPG training several times per week until 12 training sessions are completed. The 12th session internal evaluation performance measures for the 5 core games and one added EF game will provide the endpoint for BPG dynamic assessment (gain in BPG performance from session 1 to session 12). Because BPG training will occur on a tablet connected to the internet through the mobile network, performance data can be uploaded for analysis via the MSU GEL lab principal server, as done in the Kayunga Uganda CCRT study with BPG ¹.

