5.3 Study Outcomes and Exposure Variables of Interest

Primary Outcome: Correlation between coefficients of gold-standard measures (KABC-II, TOVA, CogState) and BPG scores. We will evaluate the concurrent validity by computing correlation coefficients of the BPG and "gold standard" measures at intake, 1 and 7 months after intake.

Exposure Variables of Interest:

BPG package

BPG executive function reasoning/planning game (to be developed)

HIV status (infected, exposed, unexposed)

Nutritional and growth history (PROMISE NeuroDev R01 HEU and HUU cohorts)

ARV exposure and clinical response to treatment history (HIV cohort)

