5.6.1 Randomization procedure

Systematic randomization will be used to assign children within each HIV exposure cohort into BPG training or wait-list conditions. Lists of all children within each cohort will be generated and a simple random sampling will be used to assign children into treatment groups. The first child will be assigned to BPG and the next to wait list. For the HEU and HUU cohorts, separately, two sets of random numbers ranging from 001 to 120 will be generated, and the first 60 random numbers drawn from each set will be assigned to start BPG. The second 60 numbers from HEU and 60 from HUU drawn will be assigned to the wait list condition.

A third set of random numbers ranging from 01 to 60 will be generated for the HIV+ group, the first 30 numbers drawn will be assigned to the BPG group. The second 30 numbers drawn from the HIV+ cohort will be assigned to the wait list condition.

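### The lead outcomes in Sections 5.3 and 5.6.5 are not ranked, and Section 7 attributes pre-post gains to training without naming the randomised arm

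*Combined protocol and SAP*

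**What the plan says.** **Outcome labels.** Section 5.3 reads: "Primary Outcome: Correlation between coefficients of gold-standard measures (KABC-II, TOVA, CogState) and BPG scores", evaluated at intake, 1 and 7 months. The schema also has a Primary Outcome, worded as a goal: "To establish the validity of BPG as a measure of neurodevelopment in at-risk children". Section 5.6.3 calls seven KABC-II global scores and six TOVA variables primary, and three CBCL scores principal. Section 5.6.5 then adds: "We will also use gain scores pre- to post-training for our gold standard of neuropsychological tests as our principal performance outcomes in the present study". No sentence ranks these.

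**Design.** Section 5.1 says that "children will be randomized to start BPG trainings (50% of sample) or to a wait-list condition", and Section 5.6.1 that "Systematic randomization will be used to assign children within each HIV exposure cohort into BPG training or wait-list conditions". Under Section 5.1, every child takes the gold-standard battery at intake, and the full sample returns for it after the training period. Both arms therefore have intake and post-training scores.

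**Analysis.** Section 7.1.1 describes the design as observational. Section 7.1.2 plans the following:
- correlations between BPG and gold-standard scores;
- effect-size statistics, including the standardised response mean (SRM) and Guyatt's version of it;
- for Aims 1 and 2, a mixed model (LME) of gold-standard scores at months 1 and 7, with BPG measures, time, risk factors and number of earlier test sessions as covariates;
- for Aim 3, a mixed model with intake, month 1 and month 7 as repeated outcomes and time as a categorical factor.

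The Aim 3 text expects scores to rise from intake to month 1 because of training, and to change more slowly afterwards. Neither model names the randomised arm or an arm-by-time term. The Aims 1 and 2 model does not name the intake gold-standard score as a covariate.

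**The concern.** The 5.3 outcome asks whether BPG measures what the established tests measure. The 5.6.5 outcome records how far scores on the established tests move after training. These are different questions. Without a stated order, a reader of the results cannot tell which finding was meant to carry the study.

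The second issue follows from the first. Once gains on the gold-standard tests are put forward as leading outcomes, and Section 7 credits them to training, the plan needs a comparison that can support that attribution. The randomised wait-list arm provides it, but the analysis section does not use it. At stake is a statement that training raised scores which would rest on pre-post change alone. Repeated testing and six or more weeks of growing older could produce part or all of that change.

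**Working it through.** **1. The plan's own sample size.** Inputs from Section 7.1: d = 0.26 for HEU versus HUU, d = 0.31 for HIV versus either, two-sided 0.05, power 0.80. By the normal approximation, n = 2(1.960 + 0.842)²/0.26² = 233 per group, against the 240 planned. Power at 240 versus 240 is 0.813. For 120 versus 240 at d = 0.31, power is 0.792, close to the stated 0.80. The figures reproduce. They rest on differences by HIV status, not on a correlation or a gain, so nothing below changes 600.

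**2. Size of the randomised arms.** From Section 5.6.1, taking its number lists as one site's: 60 + 60 + 30 = 150 children start BPG and 150 wait. Over two sites this gives 300 versus 300, of which the HIV cohort supplies 60 versus 60.

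**3. What the pooled change estimates.** Let p be the mean change from intake to post-test without training (practice, maturation), and d the added effect of training.
- Trained arm: p + d. Wait-list arm: p.
- Pooled at 1:1: ½(p + d) + ½p = p + d/2.
- Difference between arms: (p + d) − p = d.

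A time effect with no arm term returns p + d/2. If the Aim 3 model were instead limited to trained children, it would return p + d. Neither isolates d.

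**4. Precision of the arm contrast.** Take SD = 1 at both times and pre-post correlation r.
- Gain-score variance: 1 + 1 − 2r = 2(1 − r).
- Variance of the post-training score adjusted for intake: 1 − r².
- Ratio, adjusted to gain: (1 − r²)/[2(1 − r)] = (1 + r)/2.

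The documents give no r, so it is assumed. The detectable difference at 80% power, two-sided 0.05 and no dropout, in score SDs, is 2.802 × √(2/n per arm) × √variance.

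| r | Variance ratio | Extra children for gain score, 2/(1+r) − 1 | 300 v 300: gain / adjusted | HIV cohort, 60 v 60: gain / adjusted |
|---|---|---|---|---|
| 0.6 | 0.80 | 25% | 0.205 / 0.183 | 0.457 / 0.409 |
| 0.7 | 0.85 | 18% | 0.177 / 0.163 | 0.396 / 0.365 |
| 0.8 | 0.90 | 11% | 0.145 / 0.137 | 0.323 / 0.307 |

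Over a wider range, the extra requirement runs from 54% at r = 0.3 to 5% at r = 0.9.

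**The case against.** **The labels are loose, not rival.** Only Section 5.3 and the schema carry the heading Primary Outcome, and both concern validity. Section 5.6.5 says principal, and Section 5.6.3 uses primary or principal for one instrument after another. This stands. A reader might infer two declared primary endpoints from which the favourable one could be chosen. The text does not go that far: it shows unranked labels that need reconciling.

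**Section 7 does analyse change.** The Aim 3 model contains the intake-to-month-1 contrast, and the SRM statistics are built on change. This also stands. It would be wrong to say that gains have no analysis. What is absent is the comparison by arm.

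**The gain is not shown to be a raw difference.** Section 5.6.5 gives no formula, Section 7.1.2 plans standardised scores, and the table of outcomes by game that Section 5.6.5 cites cannot be read in the available text. The form of the gain score is therefore left open here.

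**The aim is validation, not efficacy.** The text just before the 5.6.5 sentence reports that gains tracked patients' clinical state, so the gain may be meant as a measure to relate to HIV and health factors. For that use, the variance formula does not show that adjustment is better: between non-randomised HIV-status groups, gain and baseline-adjusted analyses answer different questions. This limits the precision argument to the arm contrast. It does not remove the attribution problem, because Section 7.1.2 itself credits the early gain to training.

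**Conclusion.** The point holds in two limited parts.

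First, the plan gives several leading-outcome labels (schema, 5.3, 5.6.3, 5.6.5) and no hierarchy.

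Second, Section 7 attributes the intake-to-month-1 gain to training without naming the randomised arm. As written, the change pools trained and wait-list children and cannot separate training from retest practice. This conclusion needs no numerical assumption beyond 1:1 allocation.

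The precision gain from adjusting for intake is secondary and modest: 10% to 20% less variance for assumed r of 0.8 to 0.6, with equal SDs at both times. It applies to the randomised contrast only. A reader might infer that the study is undersized or that its HIV-status comparisons lose precision. Neither follows, because the sample size reproduces on its own basis and those comparisons are not randomised.

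**What to change.** 1. Keep the Section 5.3 correlations as the only primary outcome. Reword Section 5.6.5 so that the gold-standard gains are secondary, and state how the gain is computed. Bring the labels in the schema and Section 5.6.3 into line.
2. In Section 7.1.2, for any statement about a training effect, specify the post-training gold-standard score regressed on randomised arm, with the same test's intake score, age, cohort and site as covariates. An arm-by-time term in the Aim 3 mixed model is an acceptable alternative. A common intake mean for both arms, which randomisation justifies, then keeps the precision of baseline adjustment.
3. If no training effect is to be claimed, remove the wording that credits the early gain to training.

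The method is already familiar to the team: the preliminary study in Section 4.1 modelled the post-training KABC-II index on its pre-training value. The cost is a few sentences. It needs no new data, visits or children, because both arms already have the battery at intake and after training.
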